7.4 Subgroup Analysis

The comparison of the two treatment groups for the primary and secondary efficacy endpoints will be performed by disease type. The same ANCOVA models without disease factor as used in the main analyses will be used.

- Patients with sickle cell disease (SCD) only
- Non- SCD patients.

7.5 Sensitivity Analysis

Sensitivity analyses will be performed on the primary efficacy measure, LIC. As a sensitivity analysis, the missing data imputation will be repeated with the LOCF method being used for all drop-out patients in the deferoxamine group and the “worst value” method being used for all drop-out patients in the Ferriprox group. This imputation approach will result in the worst case scenario for the Ferrirox group. In addition, the primary efficacy analysis will be repeated on a dataset involving only patients who have at least 6-month LIC data in the ITT population to assess the impact of early patient withdrawal on the results of the ITT analysis.

7.6 Exploratory Analysis

The following success criteria in LIC were used for the submission of Exjade’s NDA.

LIC at Baseline	Success, if LIC at the last measure is
2 to < 7 mg Fe/g dw	1 to < 7 mg Fe/g dw
≥ 7 to < 10 mg Fe/g dw	1 to 7 mg Fe/g dw
≥ 10 mg Fe/g dw	Decrease in LIC ≥ 3 mg Fe/g dw

The success rates for Ferriprox and deferoxamine groups will be calculated based on these success criteria and will be compared using Fisher’s exact test. It is noted that there should be no patients in the first category of 2 to < 7 mg Fe/g dw at baseline LIC because one of the inclusion criteria for this study is baseline LIC >7 mg/g dw (measured by MRJ).

In addition to the statistical analyses that have been specified in the SAP, any other exploratory analyses will be performed, if warranted, as post hoc analyses.

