However, patient's recruitment in this study has proceeded at a very slow pace and despite all our efforts over the past 4 years, the goal of enrolling a total of 300 patients has not been reached. A total of 213 patients (142 patients for Ferriprox and 71 patients for deferoxamine) are projected to have either completed the study or been withdrawn from the study by November 30, 2018. An interim analysis is planned to be performed on the data of these 213 patients. Based on the same values of non-inferiority margin and SD of the LIC measurement, but an α level of 0.0399, two-sided (Pocock's α spending method, see section 3.7 for details), this sample size (213 patients) will provide 89% power to demonstrate non-inferiority of Ferriprox to deferoxamine in this interim analysis, assuming no real difference in efficacy between the two treatments. For the subgroup analysis of only patients with sickle cell disease, the power will be 82% as there are 178 SCD patients (119 patients for Ferriprox and 59 patients for deferoxamine), which is approximately 84% of 213 patients. With the safety data of 213 patients, there is 98% chance (power) of occurrence of at least 1 SAE with an anticipated incidence rate of 2%, or 88% chance for an anticipated incidence rate of as low as 1%.

During this interim analysis, while patient enrollment has been put on hold, there will still be 17 patients who are on-going with their assigned drug treatment. All are projected to have completed the study by October, 2019. If the results of the interim analysis lead to the conclusion of non-inferiority of Ferriprox to deferoxamine, considerations will be given on early termination of the study, to avoid unnecessary exposure of patients to a clinical trial that has reached its objectives. The data from those patients up to the time of

study closure will be added to the interim dataset for the final statistical analysis of the study based on the same statistical analyses in this SAP.

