3.6 Method of Assignment to Treatment

At the baseline visit, patients will be randomly assigned to receive Ferriprox or deferoxamine in a 2:1 ratio. Stratified randomization based on disease category (sickle cell disease vs. other anemias) and on the transfusional iron input in the 3 months prior to baseline (> 0.3 mg/kg/day vs. ≤ 0.3 mg/kg/day) will be employed to ensure that the 2:1 ratio is maintained within each of the 4 strata: 1) sickle cell disease with transfusional iron input > 0.3 mg/kg/day, 2) sickle cell disease with transfusional iron input ≤ 0.3 mg/kg/day, 3) other anemias with transfusional iron input > 0.3 mg/kg/day, and 4) other anemias with transfusional iron input ≤ 0.3 mg/kg/day. Treatment assignment and drug allocation will be performed by an Interactive Voice Response System (IVRS).

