7.1 Primary Efficacy Endpoint

Primary efficacy endpoint is the change from baseline to Week 52 in LIC. Primary efficacy endpoint will be compared between the two treatment groups using an analysis of covariance (ANCOVA) model including treatment variable as the main factor, and overall average transfusional iron input during the study, baseline LIC, and stratification factors (disease category and transfusional iron input in the 3 months prior to baseline) as covariates. The 96.01% $(1 - \alpha)$, where $\alpha = 0.0399$ based on the Pocock’s α spending function for interim analysis) confidence interval (CI) of the difference (Ferriprox minus deferoxamine) in change of LIC from baseline to Week 52 (i.e., Week 52 minus baseline) between the two treatment groups

will be computed. For the demonstration of non-inferiority, the upper limit of the 96.01% CI should be no more than 2 mg/g dw.

The following SAS codes of MIXED procedure will be used to produce the differences in Least Squares (LS) Mean of change in LIC at Month 6 and Month 12 between Ferriprox and deferoxamine groups and the corresponding 96.01% confidence intervals. In the mixed model, AR (1) (autoregressive of order 1) will be used for the covariance structure, and Kenward and Roger's method will be used to estimate the denominator degrees of freedom (SAS model statement option, DDFM = KR).

```

proc mixed data=LIC;
  class patient treat disease prior_iron month
  model LIC_change = treat overall_iron base_LIC disease prior_iron
    month treat*month / noint solution ddfm=kr;
  repeated month / subject=patient(treat) type=ar(1);
  lsmeans treat*month;
  estimate 'Ferriprox - Deferoxamine at Month 6' treat -1 1
    treat*month -1 0 1 0 / cl alpha=0.0399;
  estimate 'Ferriprox - Deferoxamine at Month 12' treat -1 1
    treat*month 0 -1 0 1 / cl alpha=0.0399;
run;

```

Definition of the variables in the statistical model:

LIC_change : Change in LIC from baseline to Week 5
 treat : Ferriprox or Deferoxamine
 month : Duration of treatment in month
 overall_iron : Overall total transfusional iron input (mg/kg/day) during the study
 base_LIC : LIC at baseline
 disease : Sickle cell disease or other anemias
 prior_iron : transfusional iron input in 3 months prior to baseline (≤ 0.3 mg/kg/day or > 0.3 mg/kg/day)

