14.2 Efficacy Analyses

Note: Similar tables will be produced for SCD patients only and Non-SCD patients.

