		Treatment		
	Deferiprone	Deferoxamine		
N	xxx	xxx		
		Mean ± SD (Min, Max)	Mean ± SD (Min, Max)	P-value (T-test)
Weight (kg)	xx.x ± xx.x (xx, xx)	xx.x ± xx.x (xx, xx)	0.xxxx	
Height (cm)	xxx.x ± xxx.x (xxx, xxx)	xxx.x ± xxx.x (xxx, xxx)	0.xxxx	

§For patients who had separate screening and baseline visits, height was measured only at screening

Data source: 16.2.7 Listing of vital signs including height and weight

Table 14.2.1.1 LIC at each assessment

		Treatment		
		Deferiprone	Deferoxamine	
N		xxx	xxx	P-value (T-test)
	Visit	Mean \pm SD (Min, Max)	Mean \pm SD (Min, Max)	
LIC (mg/g dw)	Baseline	xx.x \pm xx.x (xx.x, xx.x)	xx.x \pm xx.x (xx.x, xx.x)	0xxxx
	Month 6	xx.x \pm xx.x (xx.x, xx.x)	xx.x \pm xx.x (xx.x, xx.x)	0xxxx
	Month 12	xx.x \pm xx.x (xx.x, xx.x)	xx.x \pm xx.x (xx.x, xx.x)	0xxxx

Data source: 16.2.13 Listing of LIC

Table 14.2.1.2 Change in LIC at each follow-up assessment

		Treatment		
Test	Visit	Deferiprone	Deferoxamine	
N		xxx	xxx	P-value (T-test)
Change in LIC (mg/g dw) Mean \pm SD (Min, Max)	Month 6	xx.x \pm xx.x (xx.x, xx.x)	xx.x \pm xx.x (xx.x, xx.x)	0xxxx
	Month 12	xx.x \pm xx.x (xx.x, xx.x)	xx.x \pm xx.x (xx.x, xx.x)	0xxxx

Data source: 16.2.13 Listing of LIC

Table 14.2.1.3 LS Means of change in LIC from ANCOVA model at each follow-up assessment

		Treatment			
		Deferiprone	Deferoxamine	Deferiprone minus Deferoxamine	96.01% C.I.
N		xxx	xxx	xxx	
	Visit	LS Mean \pm SE	LS Mean \pm SE	LS Mean \pm SE	
LIC (mg/g dw)	Month 6	xx.x \pm xx.x	xx.x \pm xx.x	xx.x \pm xx.x	(xx.x, xx.x)
	Month 12	xx.x \pm xx.x	xx.x \pm xx.x	xx.x \pm xx.x	(xx.x, xx.x)

Data source: 16.2.13 Listing of LIC

Table 14.2.1.4 Trend analysis for LIC over time

	Deferiprone	Deferoxamine	Deferiprone minus Deferoxamine	P-value
Slope: Mean \pm SE	xx.x \pm xx.x	xx.x \pm xx.x	xx. x \pm xx.x	0.xxxx

Data source: 16.2.13 Listing of LIC

Table 14.2.1.5 Success rate in LIC based on the submission of Exjade's NDA.

	Treatment		
	Deferiprone	Deferoxamine	P-value (Fisher's exact test)
Success rate	xx.x %	xx.x%	0.xxxx

Data source: 16.2.13 Listing of LIC

Table 14.2.2.1 Cardiac MRI T2* at each assessment

		Treatment		
		Deferiprone	Deferoxamine	
N		xxx	xxx	P-value (T-test)
	Visit	Mean \pm SD (Min, Max)	Mean \pm SD (Min, Max)	
Cardiac MRI T2* (ms)	Baseline	xx.x \pm xx.x (xx.x, xx.x)	xx.x \pm xx.x (xx.x, xx.x)	0.xxxx .
	Month 6	xx.x \pm xx.x (xx.x, xx.x)	xx.x \pm xx.x (xx.x, xx.x)	0.xxxx
	Month 12	xx.x \pm xx.x (xx.x, xx.x)	xx.x \pm xx.x (xx.x, xx.x)	0.xxxx

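### The exploratory LIC success-rate comparison should give an adjusted difference with a confidence interval, not only two percentages and a Fisher p-value

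*SAP*

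**What the plan says.** SAP 7.6 borrows success criteria from another chelator's marketing application. For a baseline LIC from 7 to below 10 mg/g dw, the last LIC must lie between 1 and 7. For a baseline of 10 or more, the criterion is "Decrease in LIC ≥ 3 mg Fe/g dw". The comparison is then set out: "The success rates for Ferriprox and deferoxamine groups will be calculated based on these success criteria and will be compared using" Fisher's exact test. No covariate, stratum, effect measure, interval or significance level is named. The shell headed "Table 14.2.1.5 Success rate in LIC based on the submission of" the other product's application (SAP 17) has one success rate per arm and a Fisher p-value. It has no counts, difference, ratio or interval.

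The continuous version of the same endpoint is treated differently. SAP 7.1 adjusts for iron input during the study, "baseline LIC, and stratification factors (disease category and transfusional iron input in the 3 months prior to baseline) as covariates", and reports a 96.01% CI. SAP 3.6 describes the design: "Stratified randomization based on disease category (sickle cell disease vs. other anemias) and on the transfusional iron input" before baseline. Baseline LIC is not a stratification factor. The section is titled "7.6 Exploratory Analysis".

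**The concern.** Two things look out of line with the rest of the plan.

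First, the trial asks whether deferiprone is acceptably close to deferoxamine. A p-value from a test of equal rates does not answer that. A result above 0.05 may be read as similarity when the data still allow a sizeable difference in either direction.

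Second, the success rule is built on baseline LIC. From 7.1 a fall of 0.1 is enough, from 9.9 a fall of 2.9 is needed, and from 10 upward a fall of 3. The SAP adjusts for baseline LIC and both stratification factors when it analyses LIC change, but for none of them when it analyses the same measurement as success or failure.

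At stake is how informative one exploratory table is. Its criteria come from another product's submission, so readers may well set the rates against that benchmark.

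**Working it through.** **Inputs from the documents.** "A total of 213 patients (142 patients for Ferriprox and 71 patients for deferoxamine"), from the SAP's sample-size text before section 3.3. The same text gives 178 SCD patients (119 and 59). Protocol 11.2.4 gives an SD of 4 mg/g dw in both arms and a deferoxamine fall of 4 mg/g dw in its lower baseline category. The success rule is in SAP 7.6, and the strata and blocks of 6 are in Protocol 4.9.

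**Assumed, because the documents do not say.** Success rates between 40% and 75%; two-sided 0.05; baseline LIC spread over 7 to 30 mg/g dw; an even split on prior iron input; a true LIC difference of 1.5 mg/g dw.

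**1. The plan's own figure.** None is stated for the success rate. The nearest is the primary power in Protocol 18.4 (79/158, margin 2, SD 4, one-sided 0.025). SE = 4 × √(1/79 + 1/158) = 0.551, and Φ(2/0.551 − 1.960) = Φ(1.669) = 0.952. The non-central t gives 0.951, against 0.95017 stated. It reproduces.

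**2. Does success depend on baseline?** Take a normal change with mean −4 and SD 4 at every baseline.
- Baseline 8 (change between −7 and −1): Φ(0.75) − Φ(−0.75) = 0.773 − 0.227 = 55%.
- Baseline 9.9 (change between −8.9 and −2.9): Φ(0.275) − Φ(−1.225) = 0.608 − 0.110 = 50%.
- Baseline 10 or more (change −3 or lower): Φ(0.25) = 60%.

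If the fall grows in proportion to baseline, the simulated rates with no treatment effect are 46 to 48% below 10 and 63 to 64% from 10 upward. So it does depend, by an amount that rests on the assumed model.

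**3. Width of the missing interval.** Half-width = 1.96 × √(p₁(1 − p₁)/142 + p₂(1 − p₂)/71).
- Both rates 50%: 1.96 × √(0.25/142 + 0.25/71) = 14.2 points.
- 75% against 60%: 1.96 × √(0.1875/142 + 0.24/71) = 13.4 points.

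**4. Fisher against an unadjusted chi-square, exact enumeration at 142/71.**

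| Deferoxamine / deferiprone rate | Fisher power | Chi-square power |
|---|---|---|
| 40% / 55% | 51.4% | 53.4% |
| 50% / 65% | 50.7% | 56.1% |
| 60% / 75% | 57.8% | 61.4% |
| 50% / 70% | 78.6% | 81.4% |

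With equal rates of 40%, 50% or 60%, Fisher's actual size is 4.0 to 4.2%; chi-square's is 4.7 to 5.1%.

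**5. Adding adjustment.** Simulation with 213 patients, 2:1 in blocks of 6 within the four strata, 3,000 runs per row. CMH was stratified by the four strata and baseline LIC below or from 10. The logistic model had treatment, baseline LIC, an indicator for baseline below 10, disease and prior iron.

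| Assumed LIC fall | Fisher | Chi-square | CMH | Logistic |
|---|---|---|---|---|
| Constant | 29.6% | 31.8% | 32.3% | 32.8% |
| Proportional to baseline | 34.7% | 37.1% | 37.7% | 39.1% |
| Proportional, 3 mg/g gap between prior-iron strata | 29.9% | 32.1% | 34.8% | 35.6% |

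Adjusted minus Fisher ranges from 2.7 points (32.3 − 29.6) to 5.7 (35.6 − 29.9). Chi-square minus Fisher is 2.2 to 2.4. Adjusted minus chi-square runs from 0.5 to 3.5. The change of test is the larger part in the first two rows. In the third, where prior iron is given a strong effect, adjustment is slightly the larger. The simulation error of one power figure is about √(0.33 × 0.67/3000) = 0.9 points. With no treatment effect, the adjusted methods keep a size of 4.4 to 5.0%.

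A second model used a mean change of −3 at baseline 15, slope −0.2 per mg/g, a 1 mg/g gap between iron strata and SD 4. For true differences of 1.5 and 2 mg/g dw, power was 41% and 63% for Fisher, 45% and 69% for chi-square, and 46% and 68 to 69% for CMH. Across repeated runs, adjustment added between 0 and about 2 points.

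**6. Chance imbalance in baseline LIC.** The no-effect gap in success between baseline categories in step 5 was 6.5 to 17.4 points. If the arms differed by 10 points in the share below 10, the rate difference would move by 0.10 × 6.5 = 0.7 to 0.10 × 17.4 = 1.7 points.

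**The case against.** The case against is strong on importance. The analysis is labelled exploratory and has no margin, level or power. The non-inferiority decision rests on the LIC change model, which is adjusted and has an interval. Fisher's test holds its level. SAP 14.2 adds "Similar tables will be produced for SCD patients only and Non-SCD patients", so disease is at least displayed separately. SAP 17 says the final tables may depart from the shells, and SAP 7.6 leaves room for further post hoc analyses. A reader with the two rates and the LIC numbers from Table 14.1.2 can work out an unadjusted interval. The power figures rest on assumed baseline distributions and effects.

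All of that stands, and it keeps the point small. None of it commits the sponsor to an interval or a stratified comparison: separate disease tables are not a stratified test, and permission to add a column is not a plan to add one.

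A reader might go further and infer that power is lost chiefly because baseline LIC and the strata are ignored. The calculations do not support that in general: in most scenarios the larger part is Fisher's conservatism, which a plain chi-square would also remove. A reader might also infer that a chance baseline imbalance biases the result. It does not. Disease and prior iron are balanced by the stratified blocks, and imbalance in baseline LIC is random error that the test's level already covers.

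**Conclusion.** The point holds as a minor improvement. The firmest part is the missing estimate and interval. It needs only the arm sizes and a plausible range of rates: about 13 to 14 points either side at 95%, which two percentages and a p-value do not convey.

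The power argument is secondary. For a 1.5 mg/g dw difference, Fisher's test gives up roughly 3 to 6 points against CMH or adjusted logistic regression, and adjustment beyond chi-square accounts for about 0 to 3.5 of them. These figures depend on the assumed baseline spread, mean fall, iron effect and 0.05 level.

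The documents do not support reading this as a flaw in the trial's main inference. The primary LIC analysis already adjusts for baseline LIC and both stratification factors and reports a 96.01% CI, and no conclusion on non-inferiority depends on SAP 7.6.

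**What to change.** In SAP 7.6, make the comparison a logistic model with treatment, baseline LIC, disease and prior_iron. An indicator for baseline LIC below 10 could be added because the rule changes there; the model checked above had one. A CMH test is an acceptable alternative if the strata are few. There are only 213 − 178 = 35 non-SCD patients (142 − 119 = 23 on deferiprone and 71 − 59 = 12 on deferoxamine). Crossing disease with prior iron and baseline category would leave about 12/4 = 3 deferoxamine patients per non-SCD cell.

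In Table 14.2.1.5, add the adjusted difference in success rates (or the odds ratio) with its CI, and the counts of successes and patients by baseline LIC category. State the confidence level; SAP 7.1 and 7.2 use 96.01%. Fisher's p-value may stay alongside. The table should also be entered in the list in SAP 14.2.1, which stops at 14.2.1.4.

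The cost is a few lines of SAS and some extra table cells. All the variables are already collected, and neither the sample size nor the primary analysis changes.

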8 SAFETY ANALYSES

The safety data for continuous variables will be summarized using descriptive statistics, and the safety data for discrete variables will be presented as frequency tables.

The safety analyses will be performed by disease category as well: SCD patients and non-SCD patients.

8.1 Adverse Events

A summary table of adverse events will include the following information:

- number of patients exposed to study treatment
- number of patients experiencing at least one AE
- number of patients experiencing at least one severe AE
- number of patients experiencing at least one serious AE
- number of patients experiencing at least one drug-related AE
- number of deaths
- total number of patients withdrawn (and reason for withdrawal)
- number of withdrawals due to an AE

Adverse events will be coded using MedDRA. Adverse events are defined as AEs that occurred or worsened (increased in severity and/or frequency) on or after the first dose of study medication. Serious adverse events (SAEs) that occurred within 14 days after treatment discontinuation will be considered to be SAEs. Serious adverse events that occurred within 30 days after treatment discontinuation will be included in the database.

Adverse events will be summarized by treatment group using the total number of AEs and total exposure to the treatment, the total number and percent of patients who experience an AE, and the number and percent of patients who experienced an AE within each SOC (and preferred term within an SOC). AEs will also be presented by severity (mild, moderate, severe), by seriousness (serious, non-serious) and by relationship to study medication (at least possibly related, not related). The number of patients withdrawn will also be presented.

To count the number of patients who experienced each AE, patients who experienced the same AE multiple times will only be counted once for the corresponding preferred term. Similarly, if a patient experiences multiple AEs within the same SOC, that patient will be counted only once for that SOC. AEs will be tabulated presenting the SOC alphabetically, and within each SOC, preferred terms will be presented in decreasing order of the total number of patients who experienced each AE. In summaries presenting the

incidence of AEs by severity, seriousness, and relation to study medication, a patient with multiple events coded to a given preferred term or SOC will be counted once for that preferred term or SOC according to the most severe event, the most serious event, or the event with the closest relationship to study medication.

A listing of serious adverse events and a listing of withdrawals due to AEs will be presented. Patient deaths will be listed separately and discussed with patient narratives.

8.2 Physical Examination

A physical examination including head, ears, eyes, nose, throat, neck, respiratory system, general appearance, cardiovascular system, abdominal system, skin, and nervous system will be conducted any clinically significant findings will be recorded as adverse events.

8.3 Vital Signs, Weight and Height

Descriptive statistics will be presented for temperature, resting heart rate, respiratory rate, systolic blood pressure, diastolic blood pressure, weight and height at each visit. Changes from baseline to each follow-up assessment will be also summarized using descriptive statistics by treatment group.

8.4 12-Lead ECG

ECG data will be summarized using descriptive statistics at each assessment by treatment group. Change from baseline to each follow-up assessment will be also summarized using descriptive statistics by treatment group. Shift tables for clinically significant abnormality between baseline and the last assessment will be constructed by treatment group.

